**Effect of Vitamin D3 on Lung Function and Exercise
Tolerance in D3 Deficient COPD Patients**

ClinicalTrials.gov ID: NCT03781895

Document Date: December 23, 2018

PROJECT SUMMARY

Background: Chronic Obstructive Pulmonary Disease (COPD) is a major cause of morbidity and mortality throughout the world which is a preventable as well as treatable disease. It has some important extra pulmonary effects which may contribute to the magnitude of the severity of this disease. Standard therapeutic treatment alone does not optimize its remedy. Vitamin D₃ has been found to improve the physical efficiency of patients with various morbid disorders, including respiratory ailments. **Objectives:** To evaluate the effects of Vitamin D₃ on lung functions and exercise tolerance in patients with stable moderate COPD. **Methods:** For this, a prospective interventional randomized double blinded study will be carried out on 46 (eighty) vitamin D₃ deficient (serum 25 dihydroxycholecalciferol less than 30 ng/ml), male, stable (diagnosed patient, who has not experienced any acute exacerbation, hospitalizations, urgent care visits, or changes in routine medication within 4 weeks prior to study), moderate (post bronchodilator FEV₁/FVC < 0.70 of predicted value and FEV₁ = 50 to 79% of predicted value) COPD patients (age ≥ 40 years), who will be selected from the Out Patient Department (OPD) of the National Institute of Diseases of Chest and Hospital (NIDCH) and will be grouped as A (control) and B (study) groups, respectively. All the patients will be again designated as A0, A90 (with placebo) and B0, B90 (with D₃) for before and after 90 days of follow up. All the participants will be matched in terms of duration of COPD, history of smoking, occupation and socioeconomic status. Along with the standard pharmacological treatment of COPD, the patients of the 'Study group' will be prescribed for 80000 IU of oral vitamin D₃ per week for consecutive 3 months. Along with this, all patients both the groups will be advised to continue ad lib (according to their own choice) diet. At the very 1st day of the study, the lung functions will be assessed by measuring Forced vital capacity (FVC), Forced expiratory volume in one second (FEV₁), Forced expiratory ratio (FEV₁/FVC%), Peak expiratory flow rate (PEFR) and Forced mid expiratory flow of FVC (FEF_{25-75%}), with a portable digital spirometer. In addition, exercise tolerance will be assessed by change in 6 Minute Walk Distance (6MWD) in 6 Minute Walk Test (6MWT). Changes in peripheral capillary oxygen saturation (SpO₂) by Pulse Oximeter and degree of dyspnoea by Modified Borg Scale (MBS) will also be measured both before and after 6MWT to evaluate their change in both the groups. All these variables will be measured again after 90 days standard pharmacological treatment of COPD with D₃ intervention (B group) and also without D₃ intervention (A group). For statistical analysis, Chi-square test, independent sample 't' test between two groups, paired

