Alternate: Vitamin D₃ administration improves lung function and exercise tolerance in vitamin D₃ deficient stable COPD patients.

Objectives:

General Objective

To evaluate the effects of vitamin D₃ administration on lung functions and exercise tolerance in vitamin D₃ deficient male patients with stable COPD.

Specific Objectives

[figure not shown]
- To measure the FVC, FEV₁, FEV₁/FVC%, PEF and FEF_{25-75%} of vitamin D₃ insufficient male patients with stable moderate COPD, in order to assess their lung function status.
- To measure the SpO₂ at rest, in order to assess the basal oxygenation status in this group of patients.
- To determine level of dyspnea at rest, in order to assess the basal breathlessness level in the same group of patients
- To measure the 6MWD of all the patients, in order to assess their functional exercise capacity.
- To measure both the SpO₂ and level of dyspnea again after 6MWT, for the assessment of their exercise tolerance.
- To measure all these variables after 90 days standard pharmacological treatment with vitamin D₃ and also without vitamin D₃ in stable COPD patients.
- To compare the results of baseline and endline.

Methodology:

Consolidated Standard of Reporting Trials:

(Moher et al 2010)

CONSORT 2010 Flow Diagram

TYPE OF STUDY : Prospective interventional randomized double blinded study

PLACE OF STUDY : Department of Physiology, Bangabandhu Sheikh Mujib Medical University (BSMMU), Shahbagh, Dhaka

STUDY PERIOD : March 2017 to February 2018

STUDY POPULATION : Stable, moderate COPD patients with vitamin D₃ deficiency.

SAMPLE SIZE : 46

SAMPLING : Simple random sampling .

GROUPING OF THE SUBJECTS :

Group A : 23 D₃ deficient COPD patients without D₃ administration
(Control group)

A0 : On day 0

A90 : On day 90

Group B : 23 D₃ deficient COPD patients with D₃ administration
(Study group)

B0 : On day 0

B90 : On day 90

Subject Selection:

Inclusion Criteria

- Age: >40 years (Heideri 2015)
- Socioeconomic condition: Middle class (Martineau et al 2015)
- Smoking status: (Janssens et al 2010)
 - Current smoker = with history of active smoking
 - Ex-smoker = with history of 0 – 8 quit year
 - Duration = for >30 pack years
- BMI: 25 – 29.9 kg/meter-sq (Janssens et al 2010)
- COPD patients at moderate stage according to GOLD criteria with > 4 years duration (Rees et al 2013)
- Stable COPD patients (Mehrparver et al 2010)
- Vitamin D₃ deficient: 30 ng/ml (Vitamin D Council 2017)

Exclusion Criteria

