Investigator has applied for formal Clinical trials through www.Clinicaltrials.gov and was granted permission to go on with the trial (Annexure II) .On the first day of enrollment, the objectives, nature, purpose and potential risk of all the procedures used for the study will be explained in detail to each subject, with a cordial attitude giving emphasis on the benefits he might obtain from this study. He will be encouraged for voluntary participation and will be allowed to withdraw himself from the study even after participation, whenever he felt uneasy. If he agreed to be enrolled in the study, an informed written consent will be taken in a prescribed form (Annexure - IV). Detailed family history, medical history and thorough physical examination of each patient will be done and all the information will be recorded in a standard data sheet (Annexure - V). Then all the patients will be requested to attend the Department of Physiology at 9 am (about 1 and 1/2 hours after his breakfast) on the day of biochemical and spirometric examination.

On the examination day, 5 ml of venous blood will be collected and taken to the Hematology laboratory as soon as possible for the estimation of serum 25-hydroxycholecalceferol, serum glucose 2 hours after breakfast and serum creatinine. After that his height and weight will be measured and the spirometric lung function test will be done by using a portable spirometer. After getting all the biochemical and spirometric reports the final selection will be done, according to the inclusion and exclusion criteria.

Subsequently, all the eligible patients will be randomly assigned to either 'Control' or 'Study' groups and will be thoroughly informed about the objectives and detailed study procedure, once again. Then the patients will be examined for the baseline value of all the study variables in Day 1.

Again after 90 days the study variables will be collected from same 46 patients.

CONFOUNDING VARIABLES:

- Age: >40 years (Heideri 2015)
- Socioeconomic condition: Middle class (Martineau et al 2015)
- Smoking status: (Janssens et al 2010)
 - Current smoker = with history of active smoking
 - Ex-smoker = with history of 0 – 8 quit year
 - Duration = for >30 pack years
- BMI: 25 – 29.9 kg/meter-sq (Janssens et al 2010)
COPD patients at moderate stage according to GOLD criteria with > 4 years duration (Rees et al 2013)
- Stable COPD patients (Mehrparver et al 2010)
- Vitamin D₃ deficient: 30 ng/ml (Vitamin D council 2017)

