All the above mentioned variables will be similar ,statistically non significant in both the groups to ensure the minimization of their effects.

VITAMIN ADMINISTRATION :

Collection:

Vitamin D3

Ingredient

- Cholecalciferol (40,000IU)
- Microcrystalline Cellulose (58.1 gm)
- Butylated Hydroxy Toluene (0.2mg)
- Magnesium Stearate (3mg)
 - Gelatin Capsule Shell (1mg)

Dose : 80,000 IU/wk

Route : Oral

Placebo : Courtesy of Beximco Pharmaceuticals Limited Bangladesh

Ingredient : • Microcrystalline Cellulose (303.8gm) • Butylated Hydroxy Toluene (0.2mg)

- Magnesium Stearate (3mg)
- Gelatin Capsule Shell (1mg)

STUDY VARIABLES:

(1) Spirometric variables

- FVC (L) : Forced Vital Capacity
- FEV₁ (L) : Forced Expiratory Volume in 1st second
- FEV₁/FVC Ratio (%) : Forced Expiratory Ratio
- PEF_R (L/min) : Peak Expiratory Flow Rate
- FEF₂₅₋₇₅ (L/S) : Forced Expiratory Flow in the middle of FVC

(2) Oxygenation variables

- Resting SpO₂ (%) : Resting Peripheral Capillary Oxygen saturation

(3) Exercise tolerance variables

- 6MWD (meter) : Six Minute Walk Distance
- Level of Dyspnea : Modified Borg Scale

(4) Hematological variables

- 25(OH)D (ng/ml) : 25-hydroxycholecalciferol
- PTH (pmol/l) : Parathyroid hormone
- Ca²⁺ (mg/ml) : Ionic calcium
- PO₄³⁻ (mg/ml) : Ionic phosphate
- AP (U/L) : Alkaline Phosphatase

Subsequently a standard therapeutic treatment (according to GOLD guideline) (Annexure - VI) will be prescribed to all the selected stable moderate COPD patients. In addition, the patients of

the 'Study group' will be prescribed for 80000 IU of oral vitamin D₃ per week for consecutive 90 days . Along with this, all the patients of both the groups will be advised to continue ad lib (according to their own choice) diet.

Proper education will be given about drug , method of taking medication and medication plan. Afterwards, a good rapport will be built up to take time to time follow up over telephone and visiting patient's place . Schedule appointment , hotline and follow up will be maintained properly. They will be requested to attend the Department of Physiology again on the 90th day, to have the assessment of all the above-mentioned study variables

Any patient, who failed to follow the study procedure exactly during study period, will be dropped and a new one will be included to fulfill the desired total sample number. That's why extended sample should be taken to fulfill the total sample number.

Collection of blood sample (Afroza 2015):

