The 6MWT will be performed at indoors, along a long, flat, straight, enclosed corridor with a hard surface that is seldom traveled. The walking course will be 30 meter in length which will be marked every 3 meter. The turnaround points will be marked with a cone. A starting line, which marked

the beginning and end of each 60 meter lap, will be marked on the floor using brightly colored tape.

The subject will be asked to walk at his own maximal pace along the corridor from the end, covering as much ground as he can, during the allotted time, without running. He will be also advised to take rest if he will be too exhausted to continue the test. Standard phrases at regular intervals (every 60 seconds) will be used, like: “you are doing well,” “keep up the good work”. At the same time he will be also informed about the past time and how much has left before the test was completed.

If any of the subjects developed chest pain, intolerable dyspnoea, leg cramps, staggering, diaphoresis or pale appearance the test will be immediately stopped and the subject will be dropped. Again, when any subject will complete the total study procedure (according to the exact study design), he will be congratulated for good effort.

STATISTICAL ANALYSIS:

The results will be expressed as mean with standard deviation (mean \pm SD).

The data will be statistically analyzed by a computer with SPSS (Version 16.0) using Chi-square test,(to know the qualitative difference between the observed and expected result).Spirometric variables, oxygenation variables, exercise tolerance variables and hematological variables will be found between two groups of patients. If the variables are normally distributed , statistical analysis will be done by parametric statistical test. But if it is not normally distributed then it will be transformed into natural logarithm and again into anti logarithm, to make it normally distributed, then parametric statistical test will be done. Independent sample ‘t’ test between two groups, paired Student’s ‘t’ test within two specific measurements of different durations of each group will be done.

In the interpretation of results, ≤ 0.05 level of probability (p) will be accepted as significant.

PUBLICATION POLICY

- ❖ Scientific article to be published in a scientific journal.
- ❖ Presentation in scientific seminar or conference orally or through poster presentation.
- ❖ Website dissemination through internet version of JBSP.

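### The plan promises arms that are matched and not significantly different on confounders; the random assignment it describes cannot guarantee this, and a non-significant test at 23 per arm would not show balance

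*Combined protocol and SAP*

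**What the plan says.** The Methodology section labels the trial "Prospective interventional randomized double blinded study" and gives 23 patients to each group. Its sampling entry is "Simple random sampling", which describes how patients are drawn and not how the arms are formed. Under Study Procedure, after the laboratory and spirometry results are in and final selection is made, "all the eligible patients will be randomly assigned to either 'Control' or 'Study' groups".

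Two other places describe the arms differently. The Methods part of the Project Summary says: "All the participants will be matched in terms of duration of COPD, history of smoking, occupation and socioeconomic status". The Confounding Variables section lists age, social class, smoking, BMI, COPD stage and duration, stability and vitamin D status, and closes: "All the above mentioned variables will be similar ,statistically non significant in both the groups to ensure the minimization of their effects".

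The two lists are not the same. Occupation appears only in the Project Summary; age, BMI and vitamin D appear only under Confounding Variables. The Statistical Analysis section plans chi-square tests, independent-sample t tests between groups and paired t tests within groups, with the criterion "≤ 0.05 level of probability (p) will be accepted as significant". It describes no covariate adjustment.

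**The concern.** The documents give conflicting accounts of how the arms come to be comparable. Random assignment makes the arms comparable in expectation. It does not make every covariate similar in one sample of 46, and it cannot promise a set of p values. The closing sentence under Confounding Variables states non-significance as something that will hold, gives it the purpose of minimising the confounders' effects, and provides no mechanism for achieving it and no action if it fails.

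Two things are at stake. If someone treats the sentence as a rule to be met, group membership could come to depend on patient characteristics, and the comparison would lose the protection of randomisation. If it is only an expectation, the report is likely to argue that confounding was controlled because the baseline p values exceeded 0.05. That argument is not valid at this sample size, and the analysis contains nothing else that would deal with residual imbalance.

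**Working it through.** The plan gives no figure for balance to reproduce. Its total of 46 comes without an effect size, SD or power in the readable text, but this point does not depend on how 46 was reached.

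**Inputs**
- n = 23 per arm (Grouping of the Subjects).
- Significance level 0.05 (Statistical Analysis). Sidedness is not stated; two-sided is assumed.
- Number of variables free to differ, k (an assumption based on the lists). Middle-class status, moderate stage and stability are fixed by eligibility. Age, pack-years, BMI within its range, COPD duration and 25(OH)D give k = 5. Smoking status makes 6, and occupation (Project Summary only) makes 7.

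**1. Can random assignment guarantee non-significance?** For k independent variables, the chance of at least one significant difference under correct randomisation is 1 − 0.95^k.
- k = 5: 1 − 0.774 = 0.226
- k = 6: 1 − 0.735 = 0.265
- k = 7: 1 − 0.698 = 0.302

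These variables are probably correlated. Simulating 20,000 trials per setting with 23 per arm and equal pairwise correlation (assumed values):

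| Correlation | k = 5 | k = 7 |
|---|---|---|
| 0.3 | 21% | 27% |
| 0.6 | 17% | 21% |

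So the stated condition fails in about 17% to 30% of properly randomised trials.

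**2. Does non-significance show balance?** The largest standardised difference that stays non-significant is t(0.975, 44 df) × √(2/23) = 2.015 × 0.295 = 0.594 SD.
- The chance that a given covariate differs by at least 0.3 SD and is still non-significant is 0.315 − 0.050 = 0.265.
- As a detector of imbalance, the test has about 17% power for a difference of 0.3 SD and 38–40% for 0.5 SD.
- For a two-category variable such as current versus ex-smoker, 14/23 against 9/23 (61% v 39%) gives p = 0.14 by uncorrected chi-square and 0.24 with continuity correction.

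**3. What could an undetected imbalance do to the result?** In outcome SD units, the shift in the unadjusted difference is the covariate imbalance times its correlation with the outcome. With an assumed correlation of 0.3 to 0.5 and the imbalance at its non-significant limit:
- 0.594 × 0.3 = 0.18 SD
- 0.594 × 0.5 = 0.30 SD

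This is the worst case for one variable in one trial.

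**The case against.** The strongest reply is that the sentence describes control by restriction, clumsily worded. The Confounding Variables list repeats the inclusion criteria almost item by item, so it can be read as saying that the eligibility limits make the groups alike. Part of this stands: three of the listed items are fixed by eligibility, and restriction narrows others. If BMI were spread uniformly over 25 to 29.9 (an assumption), its SD would be 4.9/√12 = 1.41, and 0.594 SD would be only about 0.8 kg/m². But age has only a lower limit, as do pack-years and COPD duration, and restriction does not produce non-significance.

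A reader might infer that the trial will pick, move or replace patients until the baseline tests pass, so that it is not truly randomised. The documents do not support that. Study Procedure puts selection on the eligibility criteria first and random assignment second, and no section describes moving anyone for imbalance. The only replacement rule concerns patients who fail to follow the study procedure. It is true that patient characteristics are known before assignment and that the allocation of replacements is not described, but those are gaps, not evidence of interference.

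A reader might also infer that matching and randomisation are incompatible. They are not: matched-pair or stratified randomisation, or minimisation, can improve balance on a few factors. The text describes none of these, and none would guarantee non-significance on every listed variable. The flow diagram could not be seen, so this absence is a statement about the readable text only.

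**Conclusion.** The concern holds as a contradiction and an overclaim. The plan states a property of the arms that its random assignment cannot guarantee: the condition fails in about 17% to 30% of correctly randomised trials, assuming 5 to 7 free variables, correlations from 0 to 0.6 and two-sided tests at 0.05. Nor would meeting the condition show balance, since differences of up to 0.59 SD pass unnoticed at 23 per arm.

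The 0.18 to 0.30 SD shift might be read as systematic bias. It is not, if allocation is random. It is chance imbalance, already covered by the error rate of the t test, and its size rests on an assumed correlation of 0.3 to 0.5. Systematic bias would arise only if the condition were enforced by selecting or moving patients, which the documents do not say. Otherwise the harm is an unsupported statement that confounding was minimised, with chance imbalance left unadjusted.

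**What to change.** - In the Project Summary, delete the statement that participants are matched. Under Confounding Variables, delete the requirement that the listed variables be non-significant between groups. Where eligibility limits control a variable, say so.
- State that allocation stands as drawn from a list prepared in advance and is never altered because of baseline imbalance.
- Report baseline variables by arm descriptively, with no significance tests offered as proof of balance.
- Pre-specify a between-group analysis (for example analysis of covariance) adjusted for the baseline value of the outcome and, if wanted, one or two named covariates such as smoking status.
- Stratifying the list by smoking status is optional and would do little for the other variables. If blocks are used within strata, do not promise exactly 23 per arm, because unfinished blocks can leave the arms unequal.

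The cost is protocol wording and slightly more analysis work. No extra patients or procedures are needed.

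### Patients who do not follow the procedure exactly are dropped after randomisation and replaced, and no analysis set is named, so the protection of randomisation is not assured.

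*Combined protocol and SAP*

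**What the plan says.** Under Study Procedure, once eligibility is confirmed, "all the eligible patients will be randomly assigned to either" the control or the study group. Baseline measurement follows, and then: "Again after 90 days the study variables will be collected from same 46 patients".

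The follow-up paragraph after the list of study variables sets the main rule: "Any patient, who failed to follow the study procedure exactly during study period, will be dropped and a new one will be included". It adds that, for this reason, "extended sample should be taken to fulfill the total sample number". The size of that extension is not given.

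The six-minute walk section lists symptoms such as chest pain, intolerable dyspnoea and leg cramps. If any occurs, "the test will be immediately stopped and the subject will be dropped". It does not mention replacement.

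The Statistical Analysis section gives an independent t test between groups, paired t tests within groups and a 0.05 threshold. It names no analysis set, no method for missing day-90 values and no follow-up of dropped patients. The CONSORT diagram and the pages between the publication policy and the data sheet were not available for this review.

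**The concern.** Randomisation makes the arms comparable as assigned. A rule that removes patients for what they do after assignment can undo this, and refilling each arm restores the count but not the comparability. The standard of exactness is undefined, and nothing says who judges it or whether that person is blinded. With 23 per arm, one dropped patient is 1/23 = 4.3% of the arm. The rule applies to every outcome. Without day-90 data on dropped patients, no later analysis can repair the comparison.

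The walk-test rule raises a narrower issue. Walk distance and Borg dyspnoea are study variables, and some of the stopping symptoms overlap with them. At day 90, dropping such patients from the study would remove some of the worst results. A drop at the baseline test matters less, because treatment is prescribed afterwards and, under blinding, the drop should be unrelated to arm.

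**Working it through.** **Order of events.** Final selection, random assignment, baseline measurement, treatment, day 90. The exact-procedure rule acts during the study period, so it comes after assignment.

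**Inputs.** From the documents: 46 patients, 23 per arm, threshold 0.05 (taken as two-sided). The plan gives no power, effect size, SD or drop rate, so 46 cannot be reproduced, and every rate below is an assumption.

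**Exact-procedure drops, no true effect.** If a proportion p of an arm is dropped and those patients are δ SD worse than the retained ones, the retained mean lies p × δ above the full-arm mean. The spurious difference is d = δ(p₂ − p₁). Type I error comes from the non-central t with 44 df and non-centrality d/√(2/23) = d/0.295 (critical value 2.015).

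| Dropped by arm | δ (SD) | d (SD) | Non-centrality | Type I error |
|---|---|---|---|---|
| 20% v 20% | 1 | 0 | 0 | 5.0% |
| 10% v 20% | 0.5 | 0.05 | 0.170 | 5.3% |
| 10% v 20% | 1 | 0.10 | 0.339 | 6.3% |
| 10% v 30% | 0.5 | 0.10 | 0.339 | 6.3% |
| 10% v 30% | 1 | 0.20 | 0.678 | 10.2% |

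A separate simulation dropped the patients lowest on a score correlated with outcome and refilled each arm to 23. At correlation 0.5, error was 5.2% for 20% v 20% dropped, 8.6% for 10% v 30% and 9.2% for 0% v 20%. It reached 25% for 10% v 30% only when outcome alone decided who was dropped (correlation 1).

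**Walk-test drops at day 90, assumed true benefit 0.5 SD.** Let a symptom score correlate ρ with distance, with a treatment effect of 0.5ρ on that score, and drop patients below the cut that removes 10% of controls. With z the cut measured from each arm's mean score, λ = φ(z)/(1 − Φ(z)), and the retained difference is 0.5 + ρ(λ treated − λ control). For controls, z = −1.282 and λ = 0.195.

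- ρ = 0.5: treated z = −1.532, λ = 0.132; difference 0.5 − 0.5 × 0.063 = 0.47 SD; power 36%.
- ρ = 0.7: treated z = −1.632, λ = 0.111; difference 0.5 − 0.7 × 0.084 = 0.44 SD; power about 34% to 35%.
- ρ = 1 (distance alone decides): treated z = −1.782, λ = 0.085; difference 0.5 − 0.110 = 0.39 SD; power 31%.

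These powers are simulated with each arm refilled to 23. Without dropping, the non-centrality is 0.5/0.295 = 1.696 and power is 38%. With no true effect, each arm loses the same 10% on average and the test stays at about 5%.

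**The case against.** The strongest reply is that the design works against unequal dropping. The study type is given as "Prospective interventional randomized double blinded study", and the Project Summary provides a placebo: "All the patients will be again designated as A0, A90 (with placebo"). The plan also promises contact: "a good rapport will be built up to take time to time follow up over telephone" and by home visits. Three of the four unequal scenarios in the table give only 5.3% to 6.3%. This stands as a limit on the likely size. It does not remove the concern, because the plan sets no ceiling on how many may be dropped or how unequally.

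A reader might infer that replacements bypass randomisation. The documents do not say so. The assignment sentence covers all eligible patients and can be read to include later recruits. What is missing is the mechanics, and whether extra patients are additions or substitutes.

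A reader might also infer that the walk-test rule biases the between-group test or removes everyone who walks a short distance. The text supports neither. The triggers are symptoms, an exhausted patient may rest, and under blinding with no true effect the test keeps its level. *Dropped* there may mean from the test or from the study. A later sentence about patients who complete the whole procedure leans towards the study but does not settle it, and replacement after a stopped test is only inferred from the fixed total.

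Finally, an analysis set could be stated in the pages that were unavailable. If so, it would still have to be reconciled with the drop-and-replace rule.

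**Conclusion.** The point holds for the exact-procedure rule and should be corrected. The text is explicit, and nothing that could be read offsets it. The size of any bias is not known. It needs dropping that is both related to outcome and different between arms, and the figures of 5.0% to 10.2% rest on assumed rates and deficits. The documents do not show that bias will occur, so the conclusion is that protection is not assured.

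The walk-test wording is secondary. Its cost is attenuation: for an assumed 0.5 SD benefit with 10% of controls stopped, power falls from 38% to about 34% to 36% at correlations of 0.5 to 0.7, and to 31% only in the extreme case.

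The statement that the same 46 patients are measured at day 90 also does not fit with a rule that replaces some of them.

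**What to change.** 1. Delete the drop-and-replace sentence.
2. State that every randomised patient is followed to day 90 where possible, unless he withdraws consent, and is analysed in his assigned group whatever his adherence.
3. State how randomised patients without day-90 data are handled, with a sensitivity analysis, and report losses and reasons by arm. Without this, the t tests would still use completers only.
4. Randomise any extended-sample patients by the same procedure, as additions and not substitutes.
5. Keep the exact-procedure analysis as a sensitivity analysis.
6. Clarify *dropped* in the walk-test section. State that, for analysis, a stopped test does not remove the patient, and record the distance reached and the dyspnoea score. Clinical decisions to stop a test or withdraw a patient are unchanged.
7. Reconcile the same-46 statement in Study Procedure with the revised rule.

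The cost is protocol wording and day-90 follow-up of patients who would have been dropped; slightly fewer than 46 may have day-90 data. The real downside is dilution. If 20% of treated patients gained nothing (an assumption), a 0.5 SD benefit becomes 0.5 × 0.8 = 0.40 SD, the non-centrality is 0.40/0.295 = 1.356, and power falls from 38% to 26%. Randomised additions and the exact-procedure sensitivity analysis partly offset this.
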